The investigational product will be kept in a secure, limited-access storage in the ACRI research pharmacy under the direction of the research pharmacists who will be responsible for maintaining the supply according to the manufacturer's specifications, dispensing the drug for administration, and maintaining all drug accountability logs.

Study Population

We will prospectively enroll all neonates with the diagnosis of gastroschisis presenting to ACH within 12 hours after birth for whom consent is signed by the parent(s)/LAR. We anticipate enrolling 40 subjects at Arkansas Children's Hospital. All subjects that have their abdominal wall defect closed will be defined as having completed active participation in the study.

Eligibility Criteria

Inclusion criteria:

- Diagnosis of Gastroschisis
- Male or Female, any ethnicity
- Neonates [18]

Exclusion criteria:

- Primary gastroschisis repair
- Vanishing gastroschisis
- Encapsulating peritoneal sclerosis
- Infants < 2 kg and < 34 weeks gestation
- Infants > 12 hours at enrollment
- Severe hypotension, defined as either:
 - Mean arterial blood pressure (MAP) < gestational age in weeks, or
 - Systolic blood pressure (BP) < 45 or diastolic BP < 20
- Severe Hypertension defined as Systolic BP > 90 or diastolic > 60
- Culture-positive sepsis
- Known or strongly suspected inborn errors of metabolism
- Significant cardiac disorders, including cyanotic congenital heart disease, ductal-dependent congenital heart disease, and critical congenital heart disease (lesions requiring surgery or catheter-based intervention in the first year of life)
- Respiratory failure, defined as any requirement of positive pressure ventilation at the time of enrollment, or FiO₂ > 50%

Title: Direct Peritoneal Resuscitation in Gastroschisis

PI: [name]

Sponsor: UAMS

- Any other condition, that, in the opinion of the investigator, might interfere with the safe conduct of the study or place the subject at increased risk
- Lactic acidosis with at least one or more of the following:
 - Characterized by increased blood lactate levels ($> 5 \text{ mmol/L}$) on two occasions at least 6 hours apart
 - Severe metabolic acidosis with an arterial pH ≤ 7.0
 - Bicarbonate < 14 or $\text{CO}_2 < 12$
 - Base excess of $> -10 \text{ mEq/L}$
- Neonatal Acute Renal Failure, defined as serum creatinine $> 2.0 \text{ mg/dL}$ with anuria in the first 12 hours of life
- Neonatal Acute Hepatic Failure, defined as INR ≥ 3 [19]

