pCO ₂ : low*	25–30 mEq/L	25–30 mmol/L	<25 mEq/L	<25 mmol/L
pCO ₂ : high*	55–65 mEq/L	55–65 mmol/L	>65 mEq/L	>65 mmol/L
Base Excess: low*	-10 – -15 mEq/L	-10 – -15 mmol/L	>-15 mEq/L	>-15 mmol/L
Base Excess: high*	+5 – +10 mEq/L	+5 – +10 mmol/L	>+10 mEq/L	>+10 mmol/L

*Laboratory values added to the original table

Adverse Event Table – Clinical Entities [23]

	Adverse Event	Serious Adverse Event
Gastrointestinal		
Necrotizing enterocolitis		Bell Stage II or III
Intestinal perforation		Intra-abdominal free air without preceding pneumatosis
Musculoskeletal		
Fracture	Fracture treated with immobilization	Fracture with any surgical intervention needed or known lasting sequelae
Respiratory		
Respiratory failure		Initiation of mechanical ventilation or some defined change
Pneumothorax	Present but no intervention required	Intervention required (e.g., chest tubes, sclerosis therapy and/or operative)
Apnea		Requiring initiation of mechanical ventilation
Pulmonary hypertension		Present and initiation of medical therapy to treat pulmonary hypertension (e.g., nitric oxide, milrinone, sildenafil)
Neurological		
Seizure		Present and treated with anticonvulsant
Intraventricular hemorrhage		Grade 3-4
Periventricular leukomalacia		Present on imaging
Cardiology		
Hypotension		Requiring pressors
ECG QTc prolongation	460 – 485 ms	> 485 ms
Supraventricular tachycardia	Episode resolves spontaneously or with vagal maneuvers	Requiring medical drug therapy or electroconversion to revert to sinus rhythm
Infectious Disease		
Wound infection	Requiring only local intervention (e.g., topical antimicrobial)	Requiring systemic antimicrobial therapy or surgery
Urinary tract infection		Positive urine culture treated with systemic antibiotics or antifungals
Cellulitis	Requiring only local intervention (e.g., antimicrobial)	Requiring systemic antimicrobial therapy or surgery
Bloodstream infection		Positive blood culture requiring systemic antimicrobial
Meningitis		Positive cerebral spinal fluid culture requiring systemic antimicrobial
Ophthalmologic		
Conjunctivitis	Requiring only local intervention (e.g., topical antimicrobial)	Requiring systemic antimicrobial therapy or surgery
Retinopathy of prematurity	Any stage	Any stage requiring surgical or medical intervention
Otolaryngology		
Hearing impairment		Confirmed hearing loss, either unilateral or bilateral
Drug mediated		

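### The base-excess limits in the lactic acidosis exclusion and in the low base-excess SAE cells point the opposite way to the sibling limits and to the table's own AE band

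*Combined protocol and SAP*

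**What the plan says.** Two parts of the document set base-excess limits.

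- **Eligibility Criteria, exclusion list.** One item opens "Lactic acidosis with at least one or more of the following" and has four sub-items. The first begins "Characterized by increased blood lactate levels" and requires lactate above 5 mmol/L twice, at least 6 hours apart. The second is an arterial pH of 7.0 or lower. The third begins "Bicarbonate < 14 or" and adds CO2 below 12. The fourth is "Base excess of $> -10" mEq/L.
- **Appendix D, laboratory AE table.** The row "Base Excess: low" gives an AE band of -10 to -15 and an SAE limit of > -15, with the same figures in the conventional and SI columns. The row for high base excess gives an AE band of +5 to +10 and an SAE limit of > +10. Both rows carry an asterisk, explained as "Laboratory values added to the original table".

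Both places are operative. The note after the exclusion criteria requires laboratory values to be verified before DPR is given, with ineligible subjects withdrawn and possibly replaced. The Adverse Events section adopts the appendix tables as events of special interest.

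**The concern.** Base excess becomes more negative as a deficit deepens. A limit meant to catch deep deficits must therefore select values below a negative figure, and all three of these limits select values above it. Followed as printed, the rules would pick out ordinary results and let the deepest deficits through.

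The stake is the eligibility decision and the SAE count. Acid-base safety matters in this trial: the dialysate contains 40 mmol/L of lactate (Appendix A), lactic acidosis is a listed risk with its own monitoring paragraph, and the second primary objective concerns clinical and laboratory safety parameters. Eligibility may also be checked after randomization, so a misread limit could remove an infant who has already been allocated.

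**Working it through.** The plan states no calculated figure here. The check applies the printed inequalities to a range of values and compares their direction with the neighbouring limits.

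**Inputs**
- Exclusion sub-item: base excess > -10 (Eligibility Criteria).
- Low AE band: -15 to -10, with both ends taken as included, which the table does not state (Appendix D).
- Low SAE limit: > -15 (Appendix D).
- High AE band: +5 to +10; high SAE limit: > +10 (Appendix D).

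**Step 1: the text as printed**

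| Base excess (mEq/L) | Exclusion sub-item (> -10) | Low AE band | Low SAE limit (> -15) | High AE band |
|---|---|---|---|---|
| -20 | no | no | no | no |
| -15 | no | yes | no | no |
| -12 | no | yes | yes | no |
| -10 | no | yes | yes | no |
| -5 | yes | no | yes | no |
| 0 | yes | no | yes | no |
| +7 | yes | no | yes | yes |

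Three contradictions follow.
- At -12 a result is both an AE and an SAE. The same is true of every value in the AE band except exactly -15.
- At 0 a result meets the SAE limit (0 > -15), although it lies in neither AE band. The table thus counts as serious a value that it does not count as an AE.
- At -20 a result meets neither the exclusion sub-item nor the AE band nor the SAE limit.

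**Step 2: direction of the sibling limits**

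| Limit | AE band | SAE or exclusion limit |
|---|---|---|
| Exclusion: pH | - | ≤ 7.0 |
| Exclusion: bicarbonate | - | < 14 |
| Exclusion: CO2 | - | < 12 |
| Appendix D: low bicarbonate | 12 to 14 | < 12 |
| Appendix D: acidosis pH (conventional column) | 7.10 to 7.19 | < 7.10 |
| Appendix D: low pCO2 | 25 to 30 | < 25 |
| Appendix D: high base excess | +5 to +10 | > +10 |
| **Appendix D: low base excess** | **-10 to -15** | **> -15** |
| **Exclusion: base excess** | **-** | **> -10** |

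In each of the other Appendix D rows shown, the SAE range starts where the AE band ends and moves away from normal. In the low base-excess row it moves back through the AE band towards and past zero.

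**Step 3: the two readings of the exclusion item**
- *The sub-items define lactic acidosis.* No other eligibility definition is given, and the first sub-item is itself a lactate criterion, so any one sub-item is enough. A base excess of 0 then excludes (0 > -10).
- *Lactic acidosis is a separate requirement.* An infant without it is not excluded whatever the base excess. Among infants who have it, one at -5 meets the sub-item and one at -20 does not.

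The sub-item is backwards on both readings; only the first excludes a normal infant.

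**Step 4: the same figures with the signs reversed, for illustration only**

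A value of 0 meets nothing, -12 meets the exclusion sub-item and the AE band only, and -20 meets the exclusion sub-item and the SAE limit. The low AE and SAE ranges no longer overlap.

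**The case against.** A reader might infer that normal infants are excluded and that normal results are SAEs. The documents do not support that without qualification.

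- The exclusion sits under a lactic acidosis heading, so a normal infant is excluded only if the sub-items are read as the definition. That reading is plausible but not the only one.
- The SAE limit sits in a row labelled as low, beside a band written in order of increasing deficit. Staff would probably take the sign to mean a deficit larger than 15, so the intended direction is recoverable.
- No programmed eligibility check or automatic SAE flag is described, so wholesale misclassification is conjecture.

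A reader might also infer that severe acidosis would go undetected. Correctly directed limits overlap with base excess: pH, bicarbonate, CO2 and lactate for eligibility; pH < 7.10, bicarbonate < 12 and lactate > 10 mmol/L as SAEs; lactic acid > 5 mmol/L and pH < 7.1 for discontinuation. Base excess is in neither the routine nor the research laboratory lists and is not a discontinuation criterion, so the study stopping rule is unaffected.

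These arguments limit the consequence but do not remove the contradiction. The overlapping limits need not replace a base-excess limit in every case. Nor does absence from the schedule mean that no result will exist: pH is also missing from the laboratory lists yet is a discontinuation criterion, and further tests are left to the neonatologists. A misread PDF is unlikely, because the same sign appears in three places while neighbouring rows show < correctly. The asterisk says these rows were added to the source table, so that table cannot be relied on to settle the sign; it does not say who added them.

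**Conclusion.** The point holds as an internal contradiction in three printed signs: one in the exclusion list and two in the low base-excess SAE cells. It rests on the document's own sibling limits and AE band and needs no outside reference. The conclusion about the SAE cells does not depend on whether the ends of the AE band are included, apart from the value of exactly -15. The conclusion that the exclusion item is backwards does not depend on how its heading is read; the claim that a normal infant is excluded does, and is not made here. The text is wrong as written, but the point is minor. No sample size, analysis or stopping rule changes.

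**What to change.** The sponsor should reconcile the direction of the inequality in the exclusion sub-item and in both unit columns of the low base-excess SAE cells with the sibling acidosis limits and with the AE band of -10 to -15. This point questions only the direction, not the figures. In the same edit it would help to say whether the four sub-items define lactic acidosis for eligibility or apply in addition to it. Any eligibility checklist or SAE form built from this text should be checked for the same sign; those forms are not in the documents, so whether they repeat it is unknown. The cost is three characters, one clarifying phrase and a check of the forms. There is no downside.

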- Liver function test abnormalities defined as AST > 200 , ALT > 200 , GGT > 100 [19]
- Electrolyte abnormalities, defined as:
 - Sodium < 130 or $> 150 \text{ mEq/L}$
 - Potassium < 3.0 or $> 6.5 \text{ mEq/L}$
- Hyperglycemia ($> 150 \text{ mg/dL}$) or hypoglycemia ($< 40 \text{ mg/dL}$)

Note: Potentially eligible subjects may be randomized and the silo placed according to the assigned study arm before all laboratory results are available. Laboratory values will be verified for eligibility prior to administration of DPR. Any ineligible subjects will be withdrawn from the study and may be replaced.

Randomization

The randomization schedule will be generated by the biostatistics department and the Principal Investigator (PI) will maintain a randomization log listing the subjects' ID and study arm assignment. Subjects will be randomized to either the DPR group or SoC group. If the subject is assigned to receive DPR, the ACRI Research Pharmacist will dispense the 1.5% Dianeal solution. The PI will calculate the dose to be distributed based on the subject's weight at the time of enrollment and administer the appropriate volume of 1.5% Dianeal solution as per instructions in the *Investigational Product* section.

Study Design and Procedures

This is a prospective double-arm study designed to evaluate the tolerability of direct peritoneal resuscitation (DPR) in neonates with gastroschisis. The experimental arm (DPR group) will receive adjuvant DPR with standard treatment for gastroschisis (staged silo closure). The control arm (SoC group) will receive standard treatment for gastroschisis only. All subjects will be placed in a silo shortly after birth and within 2 hours of admission to the NICU and subsequently serially reduced in silo with umbilical tape until the bowel contents are at the level of fascia and deemed suitable for closure.

A. SoC Group

[figure not shown]
The SoC group will be placed in silo within 2 hours of admission to the NICU per standard practice. These subjects will have no change in current clinical management by the neonatologists or pediatric surgeons and will not receive peritoneal dialysis fluid.

B. DPR Group

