All other standard care laboratory tests will be performed at the discretion of treating neonatologists.

Routine daily labs for gastroscisis patients include:

- Complete Blood Count (CBC) with differential
- Magnesium
- Renal function panel (sodium, potassium, chloride, bicarbonate/CO₂, BUN, creatinine, calcium, phosphate, albumin, glucose)

Research Laboratory Tests

Additional research labs for safety monitoring will be drawn via heelstick, central/arterial line or venipuncture per NICU standard practice. The first capture of research labs should coincide with routine labs to avoid repeat blood draws. Up to 2 mL of blood for research may be drawn each day in addition to the routine daily labs.

SoC Group

A research lab for lactate only will be drawn every 24 hrs (\pm 30 minutes) through Post-Closure Day 1.

DPR Group

Additional research labs will be drawn every 6 hrs (\pm 30 minutes) for 24 hours after the maximum dialysate infusion volume is reached, then every 12 hrs (\pm 30 minutes) through Post-Closure Day 1.

Research labs include:

- Lactate
- Sodium
- Potassium
- Glucose

Glucose via heelstick, central/arterial line or venipuncture per NICU standard practice will also be obtained within 1 hour prior to infusion and 1 hour (\pm 15 minutes) post-infusion for the first day of treatment.

The total amount of blood to be withdrawn per day, accounting for the additional research labs above for safety monitoring, will be up to 3 mL.

Ultrasound

We will perform trans-abdominal ultrasound imaging on all enrolled subjects from the time of abdominal wall closure until feedings have commenced. Additional imaging will be performed if the neonatology team has warranted a stop to feeding the neonate. This noninvasive modality will be used to determine categorization of intestinal motility. Abdominal ultrasound will be performed each morning at the bedside by the PI or other trained study personnel.

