- b. X-ray reads daily by radiology
- c. Reason and time of change in feeding regimen
- d. Stool output

15. Adverse events*

- a. The durability of treatment effectiveness as well as potential longer-term adverse events will be assessed via chart reviews of pediatric follow-up visits or follow-up phone calls up to 90 days after discharge.

Timeline

We estimate that after approval, it will take approximately 2-3 years to accrue and follow subjects as a single-site study and 6 months to analyze data and prepare manuscripts.

Calendar of Procedures and Assessments

Assessment	Screening (Day of Birth 0-12 hrs)	Staged Reduction (Day of Birth 0-24 hrs)	Day of Life 1-7	Day of Closure	Post-Closure Day 1	Post-Closure Day 2 until Discharge	Day of Discharge	Post-Discharge Follow-Up (up to 90 days)
Informed Consent	X							
Randomization	X							
Silo/JP Drain placement ¹	X							
Verify lab values for eligibility		X						
Vitals (HR, RR, BP/MAP, SpO2)	X ²	X ²	X ²	X ²	X ³	X ³	X ⁴	
Weight	X	X	X	X	X	X	X	
Routine Labs ⁵	X			X	X	X	X	
Research Labs ^{6,7}	X	X	X	X	X	X	X	
G-tube placement ⁴	X ³							
Instill DPR ⁸	X		X					
Intake/Output		X ²	X ²	X ²	X ³	X ⁴		
Glucose pre- & post-infusion ⁹	X	X	X					
Bedside ultrasound				X		X ¹⁰		
AE assessment ¹¹	X		X	X	X	X	X	
Remove OG-tube & Initiate EBM/Formula ¹						X		
Chart Review or Phone Call							X	

¹ Silo placement only or silo and JP drain placement per randomized group assignment

² Q6 hrs (± 30 min) for 48 hrs after maximum volume, then Q12 hrs (± 30 min)

³ Q12 hrs (± 30 min)

⁴ Per NICU Standard Practice

⁵ All: CBC w/ Diff, Magnesium, Sodium, Potassium, Chloride, Bicarbonate/CO₂, BUN, Creatinine, Calcium, Phosphate, Albumin, Glucose, Q24 hrs (± 30 min)

⁶ SoC Group: Lactate only, Q24 hrs (± 30 min) same time as Routine Lab

⁷ DPR Group: Lactate, Sodium, Potassium, Glucose, Q6 hrs (± 30 min) for 24 hrs after maximum volume, then Q12 hrs (± 30 min)

⁸ DPR Group: Q6 hrs (± 30 min), dwell for 1 hr, then remove excess fluid - 10 mL/kg initial bolus, then increase by 10 mL/kg up to 40 mL/kg (100 mL maximum volume)

⁹ DPR Group only: Glucose within 1 hr prior to every infusion and 1 hr (± 15 min) every post-infusion for the first day (24hrs) of treatment

¹⁰ Daily bedside ultrasound will be performed from post-closure Day 1 to time of full feeds and if feeds are stopped for any reason

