¹¹ The clinical course of each AE should be followed until resolution, stabilization, or until it has been determined that the study treatment is not the cause.

Title: Direct Peritoneal Resuscitation in Gastroschisis

PI: [name]

Sponsor: UAMS

Schedule of Procedures and Assessments

Screening (Day of Birth from 0-12 hours)

- Informed Consent
- Randomization
- Silo placement (within 2 hours of admission to the NICU)
 - JP drain placed and secured per randomization
- Vital signs: heart rate (HR), respiratory rate (RR), MAP/BP, pulse oximetry (SpO₂)
- Weight
- Routine Daily labs per NICU standard practice:
 - Complete CBC
 - Magnesium
 - Renal Function Panel (sodium, potassium, chloride, CO₂, BUN, creatinine, calcium, phosphate, albumin, glucose)
- Research lab (both groups):
 - Lactate
- G-tube placement per NICU standard practice

Staged Reduction Day 1 (Day of Birth from 0-24 hours)

- Verify laboratory values for eligibility
- Instill DPR for DPR group every 6 hrs (± 30 minutes)
- Blood glucose within 1 hour prior to infusion and 1 hour (± 15 minutes) post-infusion for the first 24 hrs of DPR
- Vital signs every 6 hrs (± 30 minutes): HR, RR, MAP/BP, SpO₂
- Weight
- Strict intake/output every 6 hrs (± 30 minutes)
- DPR Group research labs every 6 hrs (± 30 minutes):
 - Sodium
 - Potassium
 - Glucose
 - Lactate
- Adverse events

Day of Life 1 - Day of Life 7

- Instill DPR for DPR group every 6 hrs (± 30 minutes) until abdomen is closed
- Blood glucose within 1 hour prior to infusion and 1 hour (± 15 minutes) post-infusion for the first 24 hrs of DPR
- Vital signs every 6 hrs (± 30 minutes) for 48 hours after maximum dialysate infusion volume (100 mL) is reached, then every 12 hrs (± 30 minutes): HR, RR, MAP/BP, SpO₂
- Weight
- Strict intake/output every 6 hrs (± 30 minutes) for 48 hours after maximum dialysate infusion volume (100 mL) is reached, then every 12 hrs (± 30 minutes)
- Routine daily labs per NICU standard practice:
 - Complete CBC
 - Magnesium
 - Renal Function Panel (sodium, potassium, chloride, CO₂, BUN, creatinine, calcium, phosphate, albumin, glucose)

Title: Direct Peritoneal Resuscitation in Gastroschisis

PI: [name]

Sponsor: UAMS

- SoC Group research lab (every 24 hrs (\pm 30 minutes) at the same time as routine daily labs:
 - Lactate
- DPR Group research labs every 6 hrs (\pm 30 minutes) for 24 hours after maximum dialysate infusion volume (100 mL) is reached, then every 12 hrs (\pm 30 minutes):
 - Sodium
 - Potassium

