Other possible adverse reactions may include lactic-acidosis, fungal peritonitis, peritonitis bacterial, catheter-related infections, hypovolemia, hypervolemia, fluid retention, hypokalemia, hyponatremia, dehydration, hypochloremia, hypotension, hypertension, dyspnea, peritonitis, peritoneal cloudy effluent, vomiting, diarrhea, nausea, constipation, abdominal pain, abdominal distension, abdominal discomfort, Stevens-Johnson syndrome, urticaria, rash (including pruritic, erythematous and generalized), pruritus, myalgia, muscle spasms, musculoskeletal pain, generalized edema, pyrexia, malaise, infusion site pain, and catheter related complication.

Potential benefits for these subjects include earlier closure, fewer ventilator days, earlier feeding and decreased length of stay.

There will be no direct benefits to the study participants in the SoC group; however, knowledge gained from the study could potentially benefit subjects in the future as it guides us in best practices for pediatric patients with gastroschisis.

Subject Withdrawal from Study

Subjects' parent(s)/LAR may choose to withdraw from the study for any reason. Additionally, the investigator may choose to remove subjects from the study. This may occur for the following reasons:

- Serious adverse event believed to be related to investigational product
- Intolerable side effects
- Clinically significant laboratory abnormalities
- The investigator believes it is in the best interest of the subject to discontinue the study

Any subject withdrawing their consent to participate in the study or their authorization to use their protected health information will be withdrawn from the study. Neonates who are withdrawn from the study will no longer undergo any study-related procedures or data collection. Standard of care treatment will be continued.

Reasons why subjects are discontinued from the clinical trial will be documented on the Study Termination Form.

Safety Monitoring

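### Laboratory eligibility is settled after randomization, with a time point that only the DPR arm has, and removed infants are lost to follow-up, so removal can differ by arm

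*Combined protocol and SAP*

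**What the plan says.** Three sentences in the Note under Eligibility Criteria set the sequence. On order: "Potentially eligible subjects may be randomized and the silo placed according to the assigned study arm before all laboratory results are available". On timing: "Laboratory values will be verified for eligibility prior to administration of DPR". On consequence: "Any ineligible subjects will be withdrawn from the study and may be replaced". In the DPR arm, silo placement includes a drain positioned beneath the fascia (Study Design and Procedures, DPR Group).

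The visit listings are neutral as to arm. The Schedule has "Verify laboratory values for eligibility" under Staged Reduction Day 1, which covers the first 24 hours, and the Calendar has "Verify lab values for eligibility" with a single mark in the same column. Neither limits the check to one arm, and neither names the sample to be read.

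Other relevant text:

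- At screening both arms have the routine panel and one lactate. For the DPR arm, Research Laboratory Tests adds glucose that "will also be obtained within 1 hour prior to infusion and 1 hour" after it on the first treatment day.
- The lactate exclusion needs raised values "on two occasions at least 6 hours apart".
- Randomization has the PI keep the assignment log and also give the DPR.
- Subject Withdrawal from Study says "Neonates who are withdrawn from the study will no longer undergo any study-related procedures or data collection".
- Data Analysis plans a two-sample t-test with 20 per arm and does not say which infants are analysed.

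**The concern.** An infant found ineligible after randomization leaves with no primary outcome and may be replaced. If this happens equally in both arms, the comparison narrows to laboratory-eligible infants but stays balanced. If it happens more often in one arm, the groups analysed are no longer those that randomization made.

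The plan leaves room for the second case. The only event tied to the check is the first DPR dose. Someone who knows the assignment must look at the results before dosing a DPR infant, and nothing as definite prompts a look at an SoC infant. One scheduled glucose before the first infusion exists in the DPR arm only, and glucose above 150 or below 40 mg/dL is an exclusion. If infants with abnormal admission values tend to feed later, uneven removal would make DPR look better on time to full feeds, and probably on safety too. The analysis could not undo this, because the removed infants' outcomes would not have been collected.

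**Working it through.** **The plan's own figure.** Data Analysis gives 20 per arm, SD 7 days, a 6-day difference and a two-sided 5% level, and claims at least 80% power. The standard error is 7 × √(2/20) = 2.21 days, and 6/2.21 = 2.71. On 38 degrees of freedom the t-test has 75.2% power (77.4% by the normal approximation). That shortfall is a separate matter; the figures serve here only to scale the bias.

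**Assumptions.** The documents give none of these three quantities:

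- q, the share of randomized infants who are laboratory-ineligible: 5% to 20%
- D, their extra days to full feeds: 5 to 15
- r, the share of ineligible infants removed in an arm

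Removed infants are taken to be replaced, so that 20 per arm are analysed, and DPR is taken to have no true effect.

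**Formula.** The ineligible share left in an arm is f = q(1 − r)/(1 − qr). Bias in favour of DPR = D × (f in SoC − f in DPR).

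**All removed from DPR, none from SoC.** Then f is 0 in DPR and q in SoC, so the bias is q × D.

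| q | D (days) | Bias (days) | Share of 6 days | Type I error, SD fixed at 7 | Type I error, mixture simulation |
|---|---|---|---|---|---|
| 5% | 5 | 0.25 | 4% | 5.1% | 5.2% |
| 10% | 10 | 1.0 | 17% | 7.3% | 6.9% |
| 20% | 15 | 3.0 | 50% | 26.2% | 19.3% |

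The simulation (100,000 runs per case) is the better guide at the upper end. Ineligible infants left in SoC also widen that arm's spread, which the fixed-SD calculation ignores.

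**All removed from DPR, half from SoC.**

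- Low: f in SoC = 0.025/0.975 = 0.0256; × 5 = 0.13 days
- Middle: 0.05/0.95 = 0.0526; × 10 = 0.53 days
- High: 0.10/0.90 = 0.111; × 15 = 1.67 days

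With SD fixed at 7, the type I error is 5.0%, 5.6% and 11.4%.

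**Equal removal.** The two f terms cancel: bias 0 days, type I error 5.0%.

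**Removal without replacement.** Losing 2 of 20 DPR infants lowers power from 75.2% to 72.8%; losing 4 lowers it to 69.9%.

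**The case against.** The best defence is that the check is meant for everyone. The withdrawal sentence covers any ineligible subject, and the Calendar marks the pre- and post-infusion glucose as DPR only but puts no such mark on the eligibility check. Tying the check to dosing reads naturally as a safety gate. This stands: a reader might infer that only DPR infants are checked, and the documents do not say so. What remains is that the SoC arm has a 24-hour column but no named sample or prompt, and that the check follows randomization in both arms.

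A reader might also infer that the DPR arm's 6-hourly sodium, potassium, glucose and lactate give it many more chances to fail eligibility. The documents do not support that. Those draws are mainly treatment-phase monitoring, and the first is meant to coincide with routine labs. After dosing starts, values that meet the criteria under Individual Subject Discontinuation stop DPR while assessments continue. The only clearly extra test before the first dose is one glucose. The two-value lactate rule is less clear: SoC research lactate is 24-hourly, so that arm has no scheduled repeat about 6 hours after the first, and the plan does not say whether a later DPR-arm value may complete the criterion.

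Finally, the Note permits randomization before all results are in; it does not require it. If results are usually back in time, few infants are affected.

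**Conclusion.** The point holds as a gap that permits unequal removal, not as evidence that unequal removal is planned or will occur. Four features combine: a check after randomization, a time point specific to one arm, knowledge of the assignment, and loss of all outcome data on withdrawal with no stated analysis set.

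Its size cannot be taken from the documents. The range runs from negligible to half the target difference, and the upper end needs 20% ineligible, a 15-day delay and no SoC removals. The direction assumes that laboratory-ineligible infants feed later; without such a delay this mechanism gives no bias. With 20 per arm, 10% ineligible means about 2 infants in each group (20 × 0.10), so a few uneven decisions count. The change is cheap and worth making.

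**What to change.** - Apply one eligibility check to both arms, on the same laboratory set and within the same time window from admission, and before randomization where results are available.
- State how the two-value lactate criterion is applied equally in both arms. A single admission sample cannot settle it.
- For every randomized infant, keep collecting feeding, closure and discharge dates from the medical record unless consent is withdrawn.
- Make all randomized infants the primary analysis set, and exclude laboratory-ineligible infants in a sensitivity analysis.
- State how replacements are allocated, and report removals and replacements by arm.

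Leave the pre-dose safety check on giving DPR unchanged: whether an infant is dosed is separate from whether the infant is followed and analysed. The sponsor should reconcile the Note, the Calendar and Schedule, Subject Withdrawal from Study and Individual Subject Discontinuation, so that failing eligibility and stopping DPR are clearly distinct.

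The cost is protocol wording and some chart abstraction, since these dates are already in the NICU record. The downside is small: a few infants who never receive DPR stay in the analysis and slightly dilute the effect.
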